6.0 INVESTIGATIONAL PLAN

6.1. Selection of Program Population

Animal (in vitro) Part: Mice of genetic line C57/BL6 (90 ± 15 mice)

Clinical (patients) part: 90 adult patients with different types of acid reflux disease (30 ± 5 patients with non-erosive GERD, 30 ± 5 patients with erosive GERD and 30 ± 5 patients with complications thereof (Barrett's esophagus))

6.1.1 Inclusion Criteria

Animal (in vitro) Part of study:

Mice of genetic lines C57/BL6 (black) with mean weight 24 g, mean age 10 weeks, males

Clinical (patients) part of study:

1. Signed informed consent
2. Gender: Male or Female
3. Age: 18-65 years of age
3. Clinically and/or endoscopically confirmed diagnosis of GERD

6.1.2. Exclusion Criteria

Animal (in vitro) Part: None

Clinical: (patient)

1. Treatment with PPIs and/or H2RA 1 week prior to study inclusion.
2. Female patients who are pregnant, planning to become pregnant or lactating
3. Any acute diseases or conditions, exacerbations of concomitant chronic diseases (including but not limited to inflammatory bowel disease (IBD), ulcer disease etc.) at study start/inclusion and/or which are not resolved 14 days prior to study-enrolment.
4. Participation in a clinical trial in the past 3 months
5. Any condition which, in the opinion of investigator, makes the patient unsuitable for participation in the study

6.1.3. Patient completion and withdrawal

A patient who performed all visits will be considered to have completed the study.

A patient may voluntary discontinue participation in the study at any time and for any reason without explanation. Nevertheless, the investigator will make all reasonable effort to capture the reasons for withdrawal.

The investigator may also at his/her discretion discontinue the patient from participating in this study at any time.(e.g. if further participation in the study is not considered to be in the interest of the patient : if major complications of the procedures occur or in case of need to prescribe prokinetics 48 h or antacids 24h prior to esophageal pH-impedance test).

The reasons for withdrawal will be documented in the primary data source data file (patient records) and CRF.

6.2. Number of subjects to be enrolled

Animal (in vitro) Part of the study:

M1 macrophages from mice of genetic line C57/BL6 (90±15 mice) – 90±15 samples
i.e. number of laboratory sockets: 180±30 (90±15 samples in double)

Clinical (patients) Part of the study:

30±5 patients with non-erosive GERD (NERD, as confirmed by endoscopy)

30±5 patients with erosive GERD

30±5 patients with Barrett's oesophagus

6.3. Investigator Selection Criteria: N/A

6.4. Program Duration

6.4.1. Clinical part (patients) of the study:

Program duration for each patient will be approximately 7(±3) days. Duration of recruitment is planned to be 14 months, 4 months is planned for Data Analysis, 6 months – for study report/ publication preparation.

6.4.2. Animal (in vitro) part of the study

Duration of in vitro part of the study for each sample will be defined by:

- period of macrophage culture – 48 hours,
- macrophage phenotype assessment – 24 hours.

The total duration of the in vitro study to obtain one sample will be 36 hours.

6.5. Program Conduct

[figure not shown]
This is a prospective, experimental study consisting of the two parts: a clinical (patients) part and an animal (in vitro) part.

The clinical (patients) part of the study will be conducted at the Propaedeutic Clinic of Internal medicine, Gastroenterology, Hepatology of First MGMU n.a. IM Sechenov.

The animal part of the study (in vitro) will be conducted at the Moscow State University of Medicine and Dentistry.

The in vitro part of the study will be conducted in M1 macrophages from mice of genetic line C57/BL6 (90 ± 15 mice). To mirror the design of clinical part of the study and to ensure compliance with the enrolled patients' number macrophages from 30 ± 5 mice will be exposed to acid refluxate, macrophages from another 30 ± 5 mice – to biliary refluxate and from the other 30 ± 5 mice – to mixed refluxate.

Figure 1. Study design

	Visit 1	Visit 2	Visit 3	Visit 4	Visit 5
Timelines and Allowance Window	Day 1 Baseline	Day 2 (±1Day)	Day 3 (±2 Days)	Day 4 (±2 Days)	Day 5
Signed informed consent	X				
Assignment of patient identification number	X				
Inclusion and exclusion criteria assessment	X				
Allocation to the subgroups of GERD			X		
Demographics (date of birth, gender, race)	X				
Medical history	X				
Physical examination	X	X	X	X	X
FSSG assessment	X				
Blood sampling (macrophages)		X			
Hematology (RW, HIV, HbsAg, HCV)		X			
Upper gastrointestinal endoscopy with biopsy and collection of refluxate			X		
24-h esophageal pH-impedance test with esophageal high-resolution manometry				X	
Safety assessments*	X	X	X	X	X

* Any safety issues related to the invasive study procedures

6.6. Description of Activities

Visit 1 (Baseline, Day 0)

The procedures of visit:

- **Signed informed consent**

Patients considered eligible will be informed about the general aspects and procedures of the study and have to sign informed consent prior to any assessment or procedure is conducted.

- **Assignment of patient identification number**

Each patient will be assigned a two-digit patient identification number (ascending from 01 to 90).

- **Inclusion / exclusion criteria assessment**

The following criteria should be checked prior to study enrollment:

Inclusion criteria:

1. Signed informed consent
2. Gender: Male or female
3. Age: 18-65 years of age
3. Clinically and/or endoscopically confirmed diagnosis of GERD

Exclusion criteria

1. Current treatment or treatment with PPIs and/or H2RA 1 week prior inclusion
2. Female patients who are pregnant, planning to become pregnant or lactating
3. Any acute diseases or conditions, exacerbations of concomitant chronic diseases (including but not limited to inflammatory bowel disease (IBD), ulcer disease etc.) at study-start/ inclusion and/or which are not resolved 14 days prior to enrolment in the study.
4. Participation in a clinical trial in the past 3 months

5. Any condition which, in the opinion of investigator, makes the patient unsuitable for participation in the study

- **Demographics**

Includes information about date of birth, gender, race.

- **Medical history**

Medical history includes full medical information regarding GERD (duration of symptoms, results of previous examinations (upper gastrointestinal endoscopy, 24-h oesophageal pH-impedance or pH test, esophageal high-resolution manometry), previous and current treatment, comorbidities and concomitant medication, family history of the disease. Historic reports of undesirable events associated with past medications will be considered medical history.

- **Physical examination**

Includes the measurement of height, weight, blood pressure, pulse.

- **FSSG assessment**

FSSG (Frequency Scale for the Symptoms of GERD) – questionnaire with 12 questions related to acid reflux and dysmotility symptoms (See Appendix A). Questions 2,3,5, 8 and 11 are related to 'dysmotility', while other questions consider acid reflux symptoms. FSSG allows investigators to analyze different symptoms experienced by GERD patients [10]. Sum of both parts of the questionnaire will be analyzed for each patient. Permission to use the questionnaire for this study was obtained from its author/developer, professor [name].

- **Safety Assessments**

Any AEs related to the invasive study procedures, will be collected. Only undesirable effects that are deemed at least possibly related to an Abbott medication by the investigator will be forwarded to Abbott affiliate PV.

Visit 2

- **Physical examination**

Includes the measurement of blood pressure, pulse

- **Hematology (RW, HIV, Hbs-Ag, HCV)**

Blood tests for RW, HIV, Hbs-Ag, HCV are mandatory and considered standard of medical care before any interventional procedures are performed (such as endoscopy and pH-impedancemetry).

- **Blood sampling (monocytes/macrophages)**

The protocol of monocytes/macrophages isolation from venous blood

1. Blood will be collected in previously marked Vacuette system test tube (10-12 ml)
2. Blood in the test tube will be mixed with heparin (1 ml heparin – 10 ml blood)
3. Transportation of the marked test tubes in the laboratory of Cellular Biotechnology of Moscow State University of Medicine and Dentistry. The samples will be stored at temperature $+4\pm2^{\circ}\text{C}$ until transportation and will be transported in a mobile refrigerator ($+4\pm2^{\circ}\text{C}$) to the laboratory of Cellular Biotechnology of Moscow State University of Medicine and Dentistry. Laboratory address: [name]
4. Blood sample is stirred and placed into centrifuge.

5. Blood sample is centrifuged for 15 minutes at 3000 rpm.
6. After centrifugation the supernatant is separated from blood clot, in blood clot leukocytes are separated from erythrocytes, and leukocytes are placed in a pure plastic test tube.
7. Lysis buffer is prepared: 100 ml of distilled water per 0.825 g NH4Cl, 0.0037 g EDTA.
8. The leukocyte mass is mixed with 10 ml of lysis-buffer and mixed in vortex for 5 minutes (40 rpm).
9. The test tube is centrifuged for 4 min – 1000 rpm.
10. The supernatant is separated and drawn away.
11. We place 5 ml of growth medium RPMI1640 to the cell pellet and the tube is centrifuged for 4 min – 1000 rpm.
12. The supernatant is separated and the cell pellet is resuspended in 1 ml RPMI1640.
13. The cells are counted in a cell counter

- **Safety Assessments**

Any AEs related to the invasive study procedures, will be collected.

Only undesirable effects that are deemed at least possibly related to an Abbott medication by the investigator will be forwarded to Abbott affiliate PV.

Visit 3

- **Physical examination**

Includes the measurement of blood pressure, pulse

- **Upper gastrointestinal endoscopy with biopsy and collection of different types of refluxate.** All patients will undergo an upper gastrointestinal endoscopy with biopsy and

collection of different types of refluxate. The procedure should be performed on an empty stomach standard technique of anesthesia; 10% lidocaine solution). The examination includes analysis of esophageal mucosa, expression of inflammatory changes, location, size, number of mucosal defects (erosions, ulcers, strictures, hemorrhages), as well as the appearance of the gastric and duodenal mucosa. . The modified Savary-Miller classification of esophagitis will be used to characterize changes in the esophageal mucosa.

Table 2. The modified Savary-Miller classification of esophagitis

I	single erosive or exudative lesion, oval or linear, taking only one longitudinal fold
II	noncircular multiple erosions or exudative lesions taking more than one longitudinal fold, with or without confluence
III	circular erosive or exudative lesion
IV	chronic lesions: ulcer(s), stricture(s), erosive or exudative lesion or short oesophagus, isolated or associated with lesions of grades I, II, or III
V	islands, finger-like forms or circumferential distribution of Barrett's epithelium isolated or associated with lesions of grades I to IV

For morphological research and monocyte/macrophage phenotype assessment biopsy sampling of distal esophagus will be performed according to the scheme: 4 fragments located at 12, 3, 6, 9 hours, 2 cm above the Z-line, as well as from individual foci of altered mucosa.

The refluxate samples required for the animal (in vitro) part of the study, will be placed into pure plastic test tubes and be stored at temperature +2-4 C until transportation to the Cellular Biotechnology of Moscow State University of Medicine and Dentistry. Transportation should be done at the temperature +2-4 C and be done within two hours after obtaining the refluxate.

- **Allocation to the subgroups of GERD**

Diagnosis of GERD (non-erosive and erosive) is made based on clinical symptoms (complaints of heartburn, regurgitation, belching, (non-cardiac) chest pain) and/or the results of an upper gastrointestinal endoscopy. Endoscopy should not have been done more than a month before inclusion. Diagnosis of Barrett's esophagus has to be endoscopically confirmed (incl. biopsy) and should not be older than 6 months prior to study enrolment.

Patients included into the study with a GERD diagnosis based on symptoms only and/or with an endoscopy performed more than one month ago prior to inclusion will be allocated to the subgroups on the result of endoscopy conducted at Visit 3.

- **Safety Assessments**

Information regarding complications of the procedure and patient complaints are to be collected and registered. After the procedure each patient will be placed under medical observation for at least for two hours. Any AEs related to the invasive study procedures, will be collected.

Only undesirable effects that are deemed at least possibly related to an Abbott medication by the investigator will be forwarded to Abbott affiliate PV

Visit 4

- **Physical examination**

Includes the measurement of blood pressure, pulse.

- **24-h esophageal pH-impedance test with esophageal high-resolution manometry**

To investigate number of reflux episodes and determine the type of refluxate (gastric, biliary, duodenogastric/mixed) in patients with different forms of acid reflux disease and complications thereof (Barrett's esophagus) pH-impedance test with esophageal high-resolution manometry (HRM) will be done.

Calibration of device by means of two standard buffer solutions at temperature 37 C is necessary before the 24-hr esophageal pH-impedance test is performed.

Procedure of pH impedance includes intranasal introduction of a probe into oesophagus and connection of the probe with the recording device and 24-hour wearing of the probe. Installation of the probe is carried out on an empty stomach.

High-resolution manometry (HRM) will be done with a 22-channel water-perfused catheter and Solar GI system (Medical Measurements Systems, Enschede, the Netherlands).

In GERD patients will be analyzed following HRM parameters: the distal contractile integral (DCI) and the lower esophageal sphincter resting pressure (LES RP).

24-h pH-impedance monitoring will be done in both distal oesophagus and in the stomach according to standard of practice. Esophageal pH sensor will be positioned 5 cm above the manometrically located border of the LES. Measurement with a second pH sensor in the stomach, 10cm below the LES in order to monitor intragastric acidity will be done as a standard routine procedure.

The probe is removed after 24 hours and the results from the recording unit are transferred to the computer database for further analysis.

Standard measuring parameters will be collected: percent of time when pH is less than 4, total number of reflux episodes, number of acid and alkaline reflux episodes, duration of longest reflux episode.

• Safety Assessments

Information regarding complications of the procedure and patient complaints are collected and registered. After the procedure each patient is placed under medical observation for at least two hours. Any AEs related to the invasive study procedures, will be collected. Only undesirable effects that are deemed at least possibly related to an Abbott medication by the investigator will be forwarded to Abbott affiliate PV

Visit 5

- Removing of the device for 24-h esophageal pH-impedance test.

The results from the recording unit are transferred to the computer database for further analysis.

- Physical examination

Includes the measurement of blood pressure, pulse.

- Safety Assessments

Information regarding complications of the procedure and patient complaints are collected and registered. Any AEs related to the invasive study procedures, will be collected. Only undesirable effects that are deemed at least possibly related to an Abbott medication by the investigator will be forwarded to Abbott affiliate PV.

Conduct of the Animal (in-vitro) part of the study.

The animal part of the study will be conducted in accordance with all applicable regulatory requirements: International Guiding Principles for Biomedical Research Involving Animal, APS's Guiding Principles in the Care and Use of Vertebrate Animals in Research and Training, Good Laboratory Practice.

C57/BL6 mice selected for the study would be of an appropriate genetic strain and quality, and the minimum number of animals required to obtain scientifically valid results will be defined according to the number of patients. Mice will be housed in the accredited vivarium of Moscow State University of Medicine and Dentistry to ensure that the general health of the animals is safeguarded and that undue stress is avoided. Special attention will be given to the space

allocation for each animal, and adequate standards of hygiene should be maintained as well as protection against predators, vermin, and other pests. Facilities for quarantine and isolation will be provided. Entry should normally be restricted to authorized persons. Environmental needs such as temperature, humidity, ventilation, lighting, and social interaction will be consistent with the needs of the species concerned. Noise and odor levels will be minimal. Proper facilities will be provided for the disposal of animals and animal waste. Animals will receive a supply of foodstuffs appropriate to their requirements and of a quality and quantity adequate to preserve their health, and they will have free access to potable water, unless the object of the experiment is to study the effects of variations of these nutritional requirements. Veterinary care, including a programme of health surveillance and disease prevention, will be available. Sick or injured animals should, according to circumstances, either receive appropriate veterinary care or be painlessly killed.

All mice will be infused 2 ml of 4% thioglycolates 4 days before the experiment starts. All mice will receive etherization before the experiment. Peritoneal macrophages will be isolated from peritoneal fluid of C57/BL6 mice. Peritoneal lavage fluid will be centrifuged for 4 minutes - 1000 rpm, then supernatant and cell pellet will be divided. Peritoneal macrophages will be cultured in RPMI1640 culture medium with 10% fetal bovine serum (FBS) and 100 U/ml penicillin and 100 µg /ml streptomycin on 48-well plate by 0.5×10^6 macrophages/well.

In vitro experiments on animal biological material (according to GLP and International Guiding Principles for Biomedical Research Involving Animal).

Isolation and cultivation of macrophages. Macrophages will be isolated from biological material during centrifugation at 1000 rpm within 4 minutes. The supernatant will be rejected, and the packed cells will be resuspended in RPMI-1640 nutritional medium. Then the concentration cells in RPMI 1640 will be make up to 1×10^6 /ml. [11]. After the procedure of macrophages isolation the degree of macrophages survival should be no less than 95% (a standard technique with trypan blue). Cell suspension will be distributed in the 48-well plate expected 0.5×10^6 cells per well containing 0.5 ml of RPMI 1640 medium. Macrophage cultivation will be carried out at 37°C and 5% CO2.

Determination of macrophage phenotype. At least there are three types of markers for definition of macrophages phenotype: 1) morphological marker, such as form of the cells, 2) receptor markers, such as CD25, CD80, CD163 and CD206 expression [12], and 3) functional markers, such as cytokine production or phagocytosis ability of cells [13]. Therefore we can define at least three types of macrophage phenotypes - morphological, receptor and functional. We will execute an assessment of all three types of indicators.

The morphological macrophage phenotype was defined with the use of an ordinary light microscope with magnification power 15x40. Quantity of rounded-form macrophages, typical for M1 phenotype, and fibroblast-like cells, typical for M2 phenotype [13-18] was calculated among 100 cells in 5 fields of vision in a well [19]. Rounded cells had an equal ratio of length to width or less than 2:1. If the ratio of length to width was more than 2:1, the form of a cell was regarded as fibroblast-like [20]. The morphological phenotype of macrophage population will be estimated as a ratio of absolute count of rounded-form macrophages to fibroblast-like ones.

The receptor macrophage phenotype was determined by percentage of expression of superficial and cellular receptors - CD80 for M1 phenotype and CD206 for M2 phenotype [12, 13], in the isolated macrophages during flow cytometry by means of CD80 and CD206 monoclonal antibodies [Beckman Coulter, USA; BD Pharmingen, USA]. Analysis was performed according to the producers' instructions. The receptor phenotype of macrophage population will be estimated as a ratio of CD markers expression typical for M1 phenotype and CD markers of M2 phenotype [18, 21].

The functional macrophage phenotype was estimated by cytokine (pro-inflammatory, such as IL-12 (M1 markers) and anti-inflammatory, such as IL-10 (M2 markers)) production [22]. Cytokine concentrations will be defined by flow cytometry [Beckman Coulter FC500, USA] with multiplex definition kits. The functional phenotype of macrophage population will be estimated as a ratio of functional markers of M1 and M2 phenotypes.

Determination of macrophage phenotype after exposure to human acid refluclate, human biliary refluclate and mixed human refluclate will be performed by the above mentioned methods (the part of "Determination of macrophage phenotype") and the changes vs initial results will be registered.

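### Does the plan leave open which endoscopy decides the NERD or erosive group for patients scoped within a month of inclusion?

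*Combined protocol and SAP*

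**What the plan says.** The allocation text in section 6.6 (Visit 3) bases a diagnosis of non-erosive or erosive GERD on symptoms, endoscopy or both. It sets an age limit: "Endoscopy should not have been done more than a month before inclusion". Patients without any endoscopy, or with one "more than one month ago prior to inclusion will be allocated to the subgroups on the result of endoscopy conducted at Visit 3". Barrett's esophagus has its own limit: the biopsy-confirmed diagnosis "should not be older than 6 months prior to study enrolment".

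The Visit 3 procedure applies to everyone: "All patients will undergo an upper gastrointestinal endoscopy with biopsy and" collection of refluxate. It is graded in a fixed way: "The modified Savary-Miller classification of esophagitis will be used to characterize changes in the esophageal mucosa". Grade V of that scale covers Barrett's ("islands, finger-like forms or circumferential distribution of Barrett's epithelium").

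The medical history at Visit 1 records "results of previous examinations (upper gastrointestinal endoscopy" among them) and "previous and current treatment, comorbidities and concomitant medication". The visit schedule in section 6.5 marks allocation to subgroups at Visit 3 only, without naming the endoscopy it rests on. Section 6.2 requires NERD to be confirmed by endoscopy, again without saying which one.

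**The concern.** A NERD or erosive patient scoped, say, two weeks before inclusion has two endoscopy results, and no sentence says which one decides the group. Because the text sends only patients with no recent endoscopy to the Visit 3 result, a reader may infer that a recent result stands for the rest. Two rules would then operate side by side, and some labels would come from a different examination than the one at which the biopsies were taken.

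The two results could differ. Section 6.1.2 bars acid suppressants only in the week before inclusion, so a patient scoped 30 days before inclusion could have been treated for up to 30 − 7 = 23 days in between. An erosive patient might have healed by Visit 3.

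NERD, erosive GERD and Barrett's are the groups in all three clinical primary endpoints (section 5.2). If the labels mixed two definitions, the comparisons between groups could be diluted.

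**Working it through.** **1. The two readings of the text**

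| Reading | Support | Consequence |
|---|---|---|
| Visit 3 endoscopy decides for all | Section 6.5 schedules allocation only at Visit 3; section 6.6 scopes and grades every patient then | One rule, same examination as the biopsies; no problem |
| In-window endoscopy stands, otherwise Visit 3 | One-month limit, followed by an explicit route for patients outside it | A validity window with a fallback; coherent, but the label may predate the biopsy |

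A figure in section 6.5 is not reproduced in the text available, so it could not be checked for a further statement.

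**2. Which endpoints a mismatch with Visit 3 mucosa can reach**

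- Biopsy macrophages (part of clinical endpoint 1): taken at Visit 3. Affected.
- Blood monocytes (rest of endpoint 1): drawn at Visit 2.
- Refluxate type (endpoint 2): pH-impedance test at Visit 4.
- FSSG score (endpoint 3): completed at Visit 1.

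Mixed labels could in principle touch any comparison by group. The specific fault, a label that does not describe the tissue analysed, is confined to the biopsy part of endpoint 1.

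**3. Size of the dilution under each rule**

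The documents give no discordance rate, so the number healed, *k*, is an assumption. Set the NERD mean to 0 and the erosive mean to 1, with 30 patients labelled in each group on the earlier endoscopy, and let *k* of the erosive patients have healed by Visit 3.

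*Earlier label kept, Visit 3 mucosa taken as the truth.* The erosive group holds *k* patients who are really non-erosive: contrast = 1 − *k*/30.

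*Regrouped on Visit 3, form of disease taken as the truth.* The *k* patients join NERD, which becomes 30 + *k*: contrast = 1 − *k*/(30 + *k*).

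| *k* | Earlier label kept | Regrouped on Visit 3 |
|---|---|---|
| 3 | 1 − 3/30 = 0.90 | 1 − 3/33 = 0.91 |
| 5 | 1 − 5/30 = 0.83 | 1 − 5/35 = 0.86 |

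Under the first rule NERD is untouched, so the Barrett's–NERD comparison does not move. Under the second, the NERD mean rises by 3/33 = 0.09 or 5/35 = 0.14 of the erosive–NERD difference, and the Barrett's–NERD comparison shifts with it.

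**4. Against sampling error**

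Assume a true difference of 0.8 SD. With *k* = 3, the loss is 0.8 × 3/30 = 0.08 SD with the earlier label and 0.8 × 3/33 = 0.07 SD after regrouping.

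The 95% CI half-width for a difference in means, in SD units, is t(0.975, n₁ + n₂ − 2) × √(1/n₁ + 1/n₂). Section 6.2 plans 30 ± 5 per group, which gives 0.569 at 25/25, 0.517 at 30/30 and 0.477 at 35/35. At *k* = 3 either loss is roughly one sixth of the half-width or less (0.08/0.517 = 0.15).

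**The case for a change.** The strongest case for a change is that the missing sentence would cost almost nothing and concerns the grouping variable of every clinical primary endpoint. Someone following the text faithfully could group the same patient either way. Exploratory status does not remove the need for one definition of the groups, since section 9.0 still labels p ≤ 0.05 as statistically significant. Extending the plan's own Visit 3 rule to everyone would also tie the label to the tissue sampled.

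Part of this stands. The sentence is missing, and a report that does not say which endoscopy was used would be harder to read.

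The rest is weaker. The clinical part runs at a single clinic (section 6.5), so divergent practice between sites does not arise. Visit 3 for all is not clearly the better rule. The rationale in section 4.0 concerns the type of GERD and its progression, and on that view a patient with recently documented erosions who has since healed is still an erosive patient. Calling that patient NERD would add a misclassification of about the size it removes, and would disturb the Barrett's–NERD comparison as well.

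A related wording point concerns Barrett's patients whose diagnosis is one to six months old. Read literally, the one-month sentence could take them in. The separate six-month limit is the more specific provision, and they are scoped, graded and biopsied at Visit 3 in any case.

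**Conclusion.** No change to the plan follows. The text is silent on one type of patient, but each available reading gives a workable rule, and the documents do not show that either produces a wrong or worse result. Choosing between them is a trade-off. The earlier result may not match the mucosa biopsied at Visit 3, which matters only for the biopsy part of clinical endpoint 1. The Visit 3 result may class healed erosive patients as NERD.

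The size cannot be established from the documents, which report neither how many patients were scoped within the month nor how often two endoscopies disagree. On the assumptions shown (healing only, 3 to 5 of 30 patients, a 0.8 SD difference), the loss under either rule is 0.07 to 0.13 SD (upper end 0.8 × 5/30), well inside the sampling error of a study that tests no hypothesis and has no calculated sample size.

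Analysts can fill the gap sensibly. Earlier endoscopy results are recorded at Visit 1 and every patient is graded at Visit 3, so the report can name the deciding endoscopy and count the disagreements without new data.

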5.2. Primary Endpoint

Animal (*in vitro*) part of the study:

To determine changes in macrophagal phenotype from baseline after exposure to three different forms of refluxate (gastric, biliary duodenogastric/mixed) by means of assessing:

- a) Morphological characteristics (quantity of M1 (round forms) and M2 (fibroblasts-like) macrophages on 100 analyzing cells in 5 non-interfering sights).
- b) Macrophagal phagocytosis activity (mean percentage of phagocytizing cells in all peritoneal macrophagal cells and mean number of bacteria ingested by macrophages)
- c) Secretory activity (ratio of proinflammatory M1 cytokines IL-1 β , IL-8, IL-12p70, IFN γ , TNF α and TNF β to anti-inflammatory M2 cytokines IL-4, IL-5 и IL-10, as well as M1/M2 cytokines IL-2 и IL-6).

- d) Receptor characteristics (ratio of superficial markers CD80 and CD 25 (M1-markers) and CD206 and CD163 (M2-markers). Changes in M1 and M2 ratios determined on the base of receptors will also be analyzed.

Clinical (patients) part of the study:

- 1. Characteristics of blood and biopsy-origin monocyte/macrophage phenotype (morphology, receptor characteristics) in patients with different types of acid reflux disease (NERD, erosive GERD) and complications thereof: Barrett's esophagus).
- 2. Number of patients with gastric, biliary, duodenogastric/mixed refluxate within each of the different patient groups (NERD, erosive GERD and complications thereof: Barrett's esophagus).
- 3. Mean FSSG scores (acid reflux related symptoms, dysmotility symptoms) in patients with gastric, duodenogastric/mixed reflux related to the three different patient subgroups (NERD, erosive GERD and complications thereof: Barrett's esophagus).

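### The morphology read in the primary endpoints has no stated masking and no field-position rule, so it stays open to observer bias that coded labels and fixed fields would cheaply reduce

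*Combined protocol and SAP*

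**What the plan says.** Section 5.2 makes morphology primary in both parts. Item (a) of the mouse part is the "quantity of M1 (round forms) and M2 (fibroblasts-like) macrophages on 100 analyzing cells in 5 non-interfering sights". Clinical primary endpoint 1 begins "Characteristics of blood and biopsy-origin monocyte/macrophage phenotype (morphology, receptor characteristics" and is to be described across NERD, erosive GERD and Barrett's esophagus.

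Section 6.6 gives the method. The instrument is an "ordinary light microscope with magnification power 15x40". The number of round and fibroblast-like cells "was calculated among 100 cells in 5 fields of vision in a well". The classification rule is numeric: "If the ratio of length to width was more than 2:1", the cell is classed as fibroblast-like. The population is then summarised as the ratio of round to fibroblast-like counts. In the mouse part, changes after refluxate exposure against the initial result are recorded. The same methods apply to human samples.

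The supplied text names no measuring device, image capture or image software for this read. It does not give the number of readers, who they are, or the order of reading. It mentions no masking and no coding of wells or slides. On field position it says only that the fields should not interfere with one another. The patient number (Section 6.6, Visit 1) and the confidentiality text (Section 8.0) protect identity. They do not conceal refluxate type or diagnosis.

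**The concern.** A count under the microscope leaves three decisions to the person counting: which fields to use, which cells within them, and on which side of 2:1 a borderline cell falls. If that person knows the exposure or the diagnosis, small and unintended differences in those decisions can follow the group. They then look exactly like a biological difference in M1/M2 balance.

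The reader could hold an expectation. Section 4.0 supposes that refluxate type influences macrophage phenotype, without saying which type favours which phenotype. Section 3.0 does cite directions by disease form: Th1 activation with erosive disease, Th2 with Barrett's, with the balance tied to M1 or M2 macrophages.

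Section 9.0 calls the study exploratory but still labels p-values of 0.05 or less as statistically significant. A differential reading error would therefore be reported as a finding, and it would distort the descriptive means as well. The plan does not mention stored images, so it provides no route to a masked re-read later.

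**Working it through.** **1. Where group knowledge could reach the reader**

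| Material | What the plan says | Consequence |
|---|---|---|
| Mouse wells | Refluxate is sent to the laboratory (6.6, Visit 3); the mouse work is done at that university (6.5) | Exposure is applied where the wells are read, and nothing separates set-up from counting |
| Patient blood | Drawn at Visit 2, allocation at Visit 3; the laboratory is at a different institution from the clinic (6.5, 6.6) | Smaller risk. It remains where a recent endoscopy or an earlier Barrett's diagnosis already fixes the group (6.6, Visit 3) |
| Patient biopsy | Taken at the Visit 3 endoscopy, the visit at which allocation is made | The group can be known when the sample is sent |

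**2. Scale of the effect**

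The plan gives no SD, effect size or power (Section 9.0 says no sample size was calculated), so it has no figure to reproduce. The following is an illustration.

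- From the documents: 30 ± 5 per group (Sections 6.2 and 6.5); threshold 0.05 and Student's t-test (Section 9.0).
- Assumed: two-sided test; no true difference; a differential shift of b = 3 cells per 100 between two groups; between-sample SD of 5 to 15 cells per 100, with 8 as a middle value.

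Noncentrality: δ = b / (SD × √(2/n)). The false-positive rate is the chance that a noncentral t with 2n − 2 degrees of freedom falls outside the critical values. For n = 30, √(2/30) = 0.2582 and the critical value on 58 degrees of freedom is 2.002.

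| SD | SD × 0.2582 | δ = 3 / that | False-positive rate |
|---|---|---|---|
| 5 | 1.291 | 2.32 | 63% |
| 8 | 2.066 | 1.45 | 30% (0.298) |
| 15 | 3.873 | 0.77 | 12% |

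At SD 8, the 3-cell shift is 3/8 = 0.375 SD. Over the planned range of group size at that SD, the rate is 25.5% at n = 25 and 34% at n = 35. At n = 30 and SD 8, a shift of 2 cells gives 16% and a shift of 1 cell gives 8%. With no differential shift the rate is the nominal 5%.

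**3. Effect on the ratio actually analysed**

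The ratio enlarges a shift in counts. At an assumed 70 round cells per 100, it moves from 70/30 = 2.33 to 73/27 = 2.70 (+16%). At an assumed 50, it moves from 50/50 = 1.00 to 53/47 = 1.13 (+13%).

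**4. What cancels and what does not**

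A tendency that affects all exposed wells equally drops out of a comparison between refluxate groups, so only a shift that differs by group matters there. It does not drop out of the before/after change within a group. Duplicate wells (Section 6.2) average random counting error, but not a shift common to both wells of a pair.

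**The case against.** The strongest defence has four parts.

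- **The 2:1 rule is a numeric criterion.** This stands in part. Most cells will be clearly on one side, and discretion is confined to borderline cells. The rule does not govern which fields and cells are counted.
- **The patient part has some natural protection.** This stands for blood, which goes to a separate institution and is drawn before Visit 3 allocation. It is incidental rather than planned. It does not cover known diagnoses or biopsies, and the plan does not say when the counts are made relative to allocation.
- **The study is exploratory, and morphology is one of several components.** This also stands. Morphology is one of four mouse items and part of one clinical endpoint. Receptor and cytokine markers are read by flow cytometry, which offers a cross-check. That lowers the priority of the point but does not answer it.
- **The size rests on assumptions.** Correct: neither the shift nor the SD has a source in the plan, and only the range is informative.

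A reader might also infer more than the text supports: that a single reader picks the fields freely, judges shape purely by eye and knows the group. The plan states none of this. The number of readers and the selection of fields are unspecified, and reading by eye is an inference from the equipment named. Being in the same laboratory does not mean being the same person. Nor do the documents show that bias will occur; they show only that nothing stated guards against it.

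**Conclusion.** The point holds as a gap in procedure, judged on the supplied text, in which Figure 1 is not reproduced. A partly subjective component of the primary endpoints has no stated masking and no rule for field position. The exposure to bias is clearest in the mouse part, smaller for patient blood, and still present for known diagnoses and for Visit 3 biopsies.

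The size is illustrative. With an assumed 3-cell differential shift at 30 per group, the false-positive rate per comparison is about 12% to 63% over SD 15 to SD 5, and about 30% at SD 8, against a nominal 5%. It would be wrong to read 30% as an estimate for this study.

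It would also be wrong to conclude that coded labels remove the problem. Visible differences between refluxates (an assumption) or the before/after sequence may still reveal some wells. Label: cheap improvement.

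**What to change.** Add a short paragraph to Section 6.6, under the determination of macrophage phenotype, stating that:

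- wells and slides carry a code that hides refluxate type and diagnosis, and the time point where practicable;
- the person who sets up the wells holds the key until the counts are locked, and does not do the counting;
- the 5 fields are taken at fixed, pre-set positions in the well.

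Coding addresses knowledge of the group, and fixed positions address field selection; both are needed. No additional patients, mice, assays or readers are required. The cost is a code list to maintain and a split of existing laboratory tasks between set-up and counting.
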